CBT Texts for PTSD & Hazardous Drinking (Project Better)

NCT05372042

Document Date: 03/12/2024

Study Protocol

Materials & Methods

This study was registered with ClinicalTrials.gov ([NCT05372042](#)) and was reviewed and approved by the University of Washington (UW) Institutional Review Board (IRB). Recruitment and data collection began in October 2022 and is expected to be completed by April 2024.

Trial Design

This study uses a 3 (message framing: gain framing vs. loss framing vs. no framing) x 2 (mindset: growth mindset vs. simple reminder) design to evaluate whether message framing and growth mindsets enhance the efficacy of the brief CBT-based text-message intervention. Following eligibility screening, participants are verified, and block randomized to intervention conditions. Assessments consist of self-report measures and will be completed at baseline, post-intervention, 1-month, and 3-months post-intervention. See Figure 1 for the study flow diagram.

Participants

The study will enroll 500 participants, age 18 years or older, who reside in Washington (WA) State, and who endorse heavy episodic drinking and exposure to a DSM-5 Criterion A traumatic event with accompanying PTSD symptoms (i.e., a score of 33+ on the Posttraumatic Stress Disorder Checklist, Civilian Version, DSM-5 [PCL-5; Weathers et al., 2013]). Additional study inclusion criteria are in Table 1. There are no exclusion criteria for study entry to maximize sample generalizability.

Recruitment

Participants will be recruited in WA State via Craigslist ads posted in all 10 statewide categories, the UW-affiliated Institute of Translational Health Sciences (ITHS) website, and the Clinical Trials website ([clinicaltrials.gov](#)). Flyers will be distributed locally in community

centers, college campuses, and businesses. A social media ad campaign (i.e., Facebook, Instagram) will be launched state-wide and will be used to target specific demographics (e.g., gender, race, ethnicity) to boost sample diversity and representation.

Measures

Measures will be exclusively self-report questionnaires to minimize participant burden and have practical remote study procedures. Demographics including age, race/ethnicity, gender, income/work status, weight (for blood-alcohol-concentration calculation), verification of cell phone ownership and willingness to receive messages, certification of English fluency, and current residential zip code (to verify WA State residency) will be assessed at screening. Trauma exposure will be assessed at screening and at 3-month follow-up (intervening trauma exposure). We will use the Life Events Checklist (LEC; Weathers et al., 2013), a 16-item measure that queries on lifetime experience of commonly reported traumatic events (e.g., sexual assault, natural disasters) and identifies the most impactful, worst event in the person's lifetime.

Co-Primary Outcome Measures. Co-primary outcome measures will be given at screening or baseline and at all follow-ups. Power calculations were based on the heavy episodic drinking outcome (see power analysis section).

Drinking behavior will be assessed via well-validated measures that provide details on drinking patterns. Heavy episodic drinking over the past month (HED: 4/5 or more drinks per single occasion for women/men) will be assessed with the Quantity Frequency scale (QF; Baer, 1993) that asks about past month peak drinking occasion, how many drinks were consumed on that occasion, and over how many hours the drinks were consumed. Typical weekly alcohol consumption will be assessed using the Daily Drinking Questionnaire (DDQ; Collins et al., 1985); participants will report the number of drinks they typically consume each day. Negative

alcohol-related consequences will be assessed via the Short Index of Problems (SIP; Miller et al., 1995), which corresponds with longer measures of drinking consequences (Forcehimes et al., 2007).

PTSD symptom severity will be assessed using the PCL-5 (Weathers et al., 2013). The PCL-5 uses the event selected as the “worst” on the LEC to index PTSD symptoms to a target trauma. The PCL-5 is commonly used and has good test-retest reliability ($rs = .82\text{-.84}$) and strong convergent validity ($rs = .85\text{-.87}$) with other PTSD measures (Blevins et al., 2015).

Secondary Outcome Measures. Secondary measures will be given at baseline and 3-month follow-up. They include the Alcohol Use Disorders Identification Test (AUDIT; Babor et al., 2001), the Depression Anxiety Stress Scales (DASS-21; Lovibond & Lovibond, 1995), the Customary Drinking and Drug Use Record (CDDR; Brown et al., 1998), the Drug Abuse Screening Test (DAST-10; Skinner, 1982), and treatment services received. A study reactions questionnaire will be given at post-intervention and 3-month follow-up to assess satisfaction with the texts and study and skill use. This measure will be used for descriptive purposes to assess the intervention’s feasibility and acceptability.

Enhancement Measures. Measures assessing avoidant coping and mindsets will be included to allow for secondary analyses to test mechanisms of action for the enhancements (Framing: approach; Mindsets: growth mindset). The 7-item avoidant coping scale assesses the extent to which individuals endorse avoiding problems and challenges (Ottenbreit & Dobson, 2004). For mindsets, a 3-item scale based on work by Dweck (1999, 2006) will assess beliefs about the changeability of PTSD symptoms, AM, and coping strategies.

Moderator Measures. To assess whether severe psychopathology associated with PTSD+ AM is a predictor of intervention response, we will assess severe mental illness and suicidality at

baseline. We will include a 4-item history of bipolar disorder and schizophrenia screening measure (Unutzer et al., 2001) and the 2-item screening version of the Columbia Suicide Severity Rating Scale (C-SSRS; Posner et al., 2011).

Procedures

Participants will follow a link included in the study advertisements to an online screening survey. The survey will start with an information statement to obtain consent, followed by self-report questionnaires assessing inclusion criteria. Participants deemed eligible from screening will be scheduled for a 5-minute verification phone call to review study procedures, allow the participant the opportunity to ask questions, obtain verbal consent, and verify participant identity. Immediately after verification, we will send baseline assessment via email. Participants will have 7 days to complete it to be officially enrolled in the study.

Once the participants complete the baseline assessment, they will be randomized using a web-based custom program. Participants are entered into the program by the project coordinator. Randomization will use stratified permuted block randomization in 8 strata with three stratified variables: PTSD severity (PCL-5 scores of 33-60 vs. ≥ 61), risk of alcohol use disorder (AUDIT scores < 20 vs. ≥ 20), and gender identity (male vs. any other gender identity). Within strata, conditions assignments are based on prior assignments to ensure balanced numbers across intervention conditions. Stratification aims to control representation of factors commonly related to intervention response across conditions.

Starting the Monday following randomization, intervention texts will be sent 3 days a week (Tuesday, Wednesday, Friday) for 4 consecutive weeks. Each participant will receive 2 texts, back-to-back, each day based on intervention condition (see below). The participant chooses what time of day they receive the texts.

A post-intervention assessment will be emailed the day after the last text has been received, and a follow-up survey will be sent 1-month and 3-months post intervention. Regular reminders will be sent to maximize completion of the follow-up surveys. All measures, procedures, and intervention delivery are done via automated text message or self-report computerized survey: study investigators and staff are not aware of individual participant intervention conditions.

Participants will be compensated for completing baseline and follow-up assessments. Compensation will be \$20 at baseline, \$25 at post, \$30 at 1-month, and \$35 at 3-month follow-up, given as Amazon gift cards. Gift card drawings after each of the follow-up assessments (five, \$50 Amazon gift cards) will be used to further encourage assessment completion. Participants will not be compensated for screening or for receiving messages.

Fraud Detection

Because this is an online study except for the verification phone call, we have thought carefully about best practices to detect possibly fraudulent participant enrollments and responses (e.g., Teitcher et al., 2015). First, we have procedures to discourage fraudulent enrollment, including masking eligibility criteria in study advertisements and screening measures and not providing compensation for completing screening. Second, we will review screening data for potential fraudulent responses prior to the verification call. This review will include use of the Qualtrics survey platform's built-in fraud detection features to identify responses potentially generated by "bots," and duplicate submissions. We will also use a reverse phone number search to identify those using Voice Over Internet Protocol (VOIP) service. We will not verify or enroll VOIP users because, based on our pilot work and early data collection in this study, they are significantly more likely to be fraudulent. Additionally, prior to verification and enrollment, we

will search participants' address, city, and zip code to confirm that the address is legitimate and within WA State. Third, the verification call serves as both a fraud deterrent and detection method. In this call, we will ask participants to provide, not confirm, their name, age, location, and contact information and will check for a match with their screening data. The call also verifies that the phone number is functioning. These procedures should decrease the likelihood of fraudulent participants enrolling.

Interventions

The CBT text-message intervention was adapted from our pilot (Bedard-Gilligan et al., 2022) in which participants received a weekly CBT skill message focused on addressing PTSD symptoms, AM, or their co-occurrence (e.g., sitting with memories and feelings [imaginal exposure – example below], approaching avoided activities [in vivo exposure—the link between traumatic events and subsequent behavioral avoidance is explained, and participants are asked to identify and engage in activities they used to enjoy], testing out activities to increase connection, pleasure, and/or competence [behavioral activation—the link between traumatic events and isolation, low mood, low self-efficacy is explained, and participants are asked to identify and engage in a new activity that can lead to positive mood, higher self-efficacy, and/or social connectedness, and reducing drinking to cope [increasing adaptive coping skill—the link between trauma symptoms and drinking to reduce them is explained, and participants are asked to identify and engaged in alternative coping strategies]). Here, participants will receive 3 messages per week for 4 weeks. All messages are one-way; participants cannot respond. Each week, participants receive a message with a skill described above, and based on randomization assignment, they will receive additional enhancements (framing and/or mindsets) via a 3 (message framing: loss vs. gain vs. no framing) x 2 (mindset: growth mindset reminder vs. not

[simple reminder]) factorial design. The additional messages were first drafted by the principal investigators ([name] & [name]) and then refined via consultation with an applied social psychologist with expertise in social psychological theories and intervention development to improve self-regulation and (mental) health. Participants' condition is held constant throughout the intervention.

Consistent with the pilot, texts will begin with a greeting from the study team (e.g., "Greetings from Project Better!"). Messages are broken into two parts to allow for more characters if participants do not have a smart phone. The first message introduces a CBT skill/coping strategy (e.g., "This week we're focusing on painful feelings and memories, which are common after stressful events. Approaching – feeling and sitting with them can actually reduce their impact. How can you approach your feelings & memories this week?" [imaginal exposure]). The second text—sent one day later—includes the message framing manipulation. Participants receive additional information about the skill, and it is framed in terms of *avoiding* future losses (e.g., "The impact of stressful events can be very difficult. To prevent things from getting worse, remember to sit with your feelings and memories this week."); *maximizing* future gains ("The impact of stressful events can be very difficult. To help make things better, remember to sit with your feelings and memories this week.") or will have *no framing* (e.g., "The impact of stressful events can be very difficult. Remember to work on sitting with your feelings and memories this week."). The third and final text – sent two days later –will include the mindset enhancement. Participants in the *growth mindset* condition receive information about our ability to change symptoms and distress, and it normalizes setbacks (e.g., "Sitting with your emotions and memories can help you change how you think and feel. Remember that setbacks are a chance to learn—you can develop these coping skills!"); those in the *no mindset* [simple

reminder] condition receive a reminder to use their skills (e.g., “Sitting with your emotions and memories can help you change how you think and feel. Remember to practice the skills.”). Text messages range in length from 124 to 265 characters. No additional resources on CBT skills are offered to participants beyond the messages.

Analysis Plan

Decision Rules

A priori decision rules will be applied to select the intervention condition that is most effective and the simplest to undergo further testing in a subsequent RCT. Consistent with best practices for studies aiming to select the most effective combination of intervention elements using a factorial design, we will use a process of elimination rather than hypothesis-testing approach in applying our decision rules (Collins, 2018). In this approach, a series of criteria will be applied, and intervention elements that fail to meet minimum criteria for efficacy will be ruled out until the strongest set of elements remains (Collins, 2018). Because Type I error is less of a concern in this approach than Type II error, significance will be defined as $p < .10$.

Decision rules are based on co-primary and secondary outcomes and do not include intervention completion rates. This decision reflects both the type of intervention (texts are passively delivered) and pilot findings (no participants withdrew from the pilot), thus non-completion rates are not expected to be a concern.

Decision rules will be as follows:

1. We will first examine main effects for PTSD and HED in a model without interaction terms. We will retain any enhancements for further consideration in Step 2 that have significant negative main effects for both outcomes. If none exist, we will retain enhancements with significant negative main effects on PTSD or HED alone.

2. We will then examine interaction effects (framing x growth mindset x time) for PTSD and HED among any enhancements with significant negative main effects. If there is one or more negative interaction terms, we will examine linear contrasts among the combinations of enhancements that are part of the interaction to determine whether adding specific enhancements leads to improvement. If this does not yield a clear conclusion in terms of the combination of effects to select, we will examine the direction and magnitude of the main and interaction effects for these conditions on secondary outcomes and participant satisfaction data. If there are no negative interaction terms, we will select any enhancements that had significant main effects and no evidence for negative impacts on outcomes.
3. If there are no positive significant interactions or main effects for either PTSD or HED, we will repeat step 1 and 2 with other co-primary and secondary outcomes in the following order: alcohol use consequences (SIP), typical weekly alcohol consumption (DDQ), depression (DASS), and anxiety (DASS).
4. If effect sizes across conditions do not differ significantly from control (no framing, simple reminder), we will choose the control given that it is the simplest condition.

Power

The co-primary outcomes for this study are HED and PTSD symptom severity. Power calculations were conducted for HED, as its lower expected average values and non-normal distribution was expected to generate a more conservative estimate of sample size relative to PTSD symptom severity. Considering a base rate of 5.93 episodes of HED per week (based on our pilot data) and $\alpha = .05$, we determined that a sample size of $N = 500$ ($n = 75$ per condition; n

= 150 per comparison) would yield $>.80$ power to detect an 18% or greater difference in number of HED episodes between any two conditions (i.e., count ratio of 0.82).

Decision rules were revisited in response to reviewer feedback when submitting our protocol for potential publication. We realized that our original approach was not fully aligned with our power analysis or our overarching goal of identifying the most efficacious *and* simplest condition. We realized that a process-of-elimination approach starting with main effects was more in line with our goal (rather than first testing the hypothesis that the combination of growth mindsets and loss-framing would be the most efficacious condition). We thus altered our decision rules from what was originally submitted to the funder and will be testing main effects (rule 1) first, followed by interaction effects (rule 2). Further, given our process of elimination approach (vs. hypothesis testing), a *p*-value cut-off of 0.10 is appropriate (Collins, 2018). The power analysis was reviewed with these changes, and we anticipate having $>.80$ power to detect even smaller main effects (i.e., a count ratio of .89).

Assessing Differences by Condition

We will use an intent-to-treat approach to analyze results and retain all available data. For each outcome, we will explore change over time by condition visually, using within-group pre-post effect sizes ($d = (M_{post} - M_{pre})/S_{dif}$), and in generalized linear mixed effects models. In mixed-effects models, we will test main effects for each enhancement (i.e., framing enhancements with no framing as the reference, growth mindset with no growth mindset as the reference) and time (baseline, post, 1-month, 3-month), and a 3-way interaction term for framing \times growth mindset \times time. We will evaluate the need for random effects for time, different specifications for time (e.g., linear, quadratic), and count regression forms of the mixed-effects model (e.g., Poisson, negative binomial, zero-inflated).

Missing Data

Mixed-effects modeling should yield unbiased estimates in the presence of missing data assuming data are missing at random—that is, missingness is only related to observed data, but not the unobserved data. We will explore missing data patterns according to baseline (time-fixed) values of variables and consider the inclusion of additional covariates that show strong associations with missingness above and beyond any other planned covariates. Should sensitivity analyses suggest that the findings may be dependent on unobserved data, we will consider the need for approaches to missing data (e.g., using the pattern-mixture approach to combine effects across missing data patterns to yield unbiased results).

References

Bedard-Gilligan, M. A., Dworkin, E. R., Kaysen, D., Ojalehto, H. J., Stappenbeck, C. A., & Lindgren, K. P. (2022). A pilot study on the feasibility, acceptability, and preliminary efficacy of a brief text message intervention for co-occurring alcohol misuse and PTSD symptoms in a community sample. *Journal of Anxiety Disorders*, 91, 102615.

Blevins, C. A., Weathers, F. W., Davis, M. T., Witte, T. K. & Domino, J. L. (2015). The posttraumatic stress disorder checklist for DSM-5 (PCL-5): Development and initial psychometric evaluation. *Journal of Traumatic Stress*, 28, 489–498. DOI: 10.1002/jts.22059

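### Step 1 tests a main effect that averages in the pre-randomisation baseline, so the coefficient that decides elimination is at most about 0.75 of a constant post-intervention effect

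*Combined protocol and SAP*

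**What the plan says.** Rule 1 under Decision Rules reads: "We will first examine main effects for PTSD and HED in a model without interaction terms". Enhancements with significant negative main effects on both outcomes go to Step 2. A fallback follows: "If none exist, we will retain enhancements with significant negative main effects on PTSD or HED alone". Significance is p < .10, and the stated reason begins: "Because Type I error is less of a concern in this approach than Type II error".

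Assessing Differences by Condition describes the mixed model. Its terms are the enhancement main effects, "time (baseline, post, 1-month, 3-month), and a 3-way interaction term for framing" by mindset by time. Baseline is thus one of the four outcome occasions. Under Procedures, randomisation follows completion of the baseline assessment. The co-primary measures are taken at screening or baseline and at every follow-up. The DASS is taken only at baseline and 3 months (Secondary Outcome Measures) and can enter through rule 3.

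No section names a baseline covariate or a common baseline mean. Missing Data refers to covariates "above and beyond any other planned covariates" but lists none.

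The Power section says that, after the rules were revised, the trial should have more than .80 "power to detect even smaller main effects (i.e., a count ratio of .89").

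**The concern.** With no enhancement-by-time term in the Step 1 model, each enhancement has a single coefficient covering all four occasions. Randomisation makes the expected difference at baseline zero, so a real effect after the texts is averaged with a null occasion. The estimate shrinks, and the extra occasion does not reduce the standard error enough to compensate.

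Step 1 is an elimination step in a plan that ranks Type II error above Type I error, and later rules do not reliably recover a missed enhancement. Step 2 examines interactions only among enhancements already retained. The single-outcome route opens only if no enhancement passes on both outcomes. Rule 3 opens only if nothing is significant for PTSD or heavy episodic drinking (HED). An effective enhancement that misses while another passes is therefore not tested again, and rule 4 defaults to control.

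**Working it through.** **Inputs from the documents.** Four occasions, one before randomisation (two for the DASS); p < .10, taken as two-sided because sidedness is not stated; base rate 5.93; count ratios .82 and .89; N = 500; 75 per condition and 150 per comparison.

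**Assumptions.** Within-person correlation ρ of .4 to .7 (not in the documents), equal between all occasions; complete data; an effect that is constant after baseline.

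**1. The plan's own power.** For one Poisson count per person, SE = √[(1 + 1/R)/(n × 5.93)] and power = Φ(|ln R|/SE − z).
- R = .82, n = 75, α = .05: .1985/.0706 = 2.809; power .802.
- R = .89, n = 150, α = .10: .1165/.0489 = 2.385; power .770.
- R = .89, n = 167 (500/3), α = .10: 2.517; power .808.

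The stated figures therefore reproduce as a single-occasion comparison with no baseline row, the .89 figure only at 167 per level and not at the stated 150.

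**2. Weight on the true effect.** The generalised least-squares coefficient recovers 1′V⁻¹d / 1′V⁻¹1, with d = (0,1,1,1). Under equal correlation this is 3/4 whatever ρ is; for the DASS, d = (0,1) gives 1/2. A mixed-model simulation of 60 data sets gave .743 (SE .028).

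On the log-count scale with flat means, ln[(1 + 3 × .89)/4]/ln(.89) = ln(.9175)/ln(.89) = .739. Other structures the plan leaves open give less (all illustrative):
- AR(1) correlation: .744 to .565.
- Random slopes: about .71 to .53.
- Retention of 100/90/85/80%: .70 to .67.
- Counts whose mean falls to 4 after baseline: about .66.

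**3. Effect on power.** Take the single-occasion variance of the contrast as 1 and the post-intervention effect as δ.
- Written test: effect 0.75δ, variance (1 + 3ρ)/4.
- Unadjusted follow-up average: effect δ, variance (1 + 2ρ)/3.
- Baseline-adjusted follow-up average: effect δ, variance (1 + 2ρ)/3 − ρ².

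Power of .80 at two-sided .10 needs noncentrality 1.645 + 0.842 = 2.486 (from unrounded values).

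| ρ | .4 | .5 | .6 | .7 |
|---|---|---|---|---|
| *Follow-up average set at .80:* written | .619 | .611 | .604 | .599 |
| baseline-adjusted | .896 | .933 | .967 | .991 |
| *Single occasion set at .80:* written | .808 | .762 | .720 | .682 |
| unadjusted follow-up average | .941 | .919 | .896 | .872 |
| baseline-adjusted | .982 | .986 | .992 | .998 |

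Example, second benchmark, ρ = .5: .75/√.625 = .949; 2.486 × .949 = 2.359; Φ(2.359 − 1.645) = .762.

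For the DASS, the written test has effect 0.5δ and variance (1 + ρ)/2. Where the unadjusted 3-month contrast has .80, the written test has .44 to .38. The adjusted contrast (variance 1 − ρ²) has .86 to .97.

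**4. If .89 is the tested coefficient.** The post-intervention ratio would then have to be (4 × .89 − 1)/3 = .853, or .89^(1/.75) = .856.

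**The case against.** The strongest reply is that the extra occasions largely offset the dilution relative to what the plan calculated. On the single-occasion benchmark the written test keeps .81 at ρ = .4. This stands, and it is why both benchmarks are shown: the .62 to .60 range is the loss against a better use of the same follow-up data, not against the plan's own calculation. Even on the milder benchmark the written test falls to .68 at ρ = .7, while the unadjusted follow-up average stays at .87 or above. Part of the advantage of the adjusted contrast is ordinary covariate gain rather than removal of the dilution.

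A second reply is that the Power section claims more than .80 for main effects, which may mean the coefficient actually tested. The text does not say, so this is a gap in documentation and not a demonstrated error. The same goes for the base rate ("Considering a base rate of 5.93 episodes of HED per week") set beside an outcome described as "Heavy episodic drinking over the past month". The two need reconciling, but the mismatch adds no weight to the dilution point.

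A reader might infer three stronger things that the documents do not support:
- **That HED power is below .80.** Absolute power depends on dispersion, correlation and the counting period, none of which is fixed for this test.
- **That a probability of missing on both outcomes can be quoted by giving PTSD and HED equal power.** The Power section expects HED to be the more conservative outcome, so equal power is not the plan's expectation.
- **That false positives rise.** The expected baseline difference is zero, so they do not.

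Stratifying on PCL-5 band, AUDIT band and gender limits chance imbalance on those factors but does not alter the dilution.

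**Conclusion.** The point holds as a dilution of the Step 1 test and should be fixed. The 0.75 is close to an upper bound: every other structure tried gave less. The 0.50 for the DASS matters mainly if rule 3 gets that far, after PTSD, HED, the SIP and the DDQ.

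The weights follow from the written model and do not depend on ρ under equal correlation. The power figures do depend on the assumed ρ of .4 to .7, complete data and a constant post-baseline effect. They compare tests with one another and do not estimate this trial's actual power. The consequence is a shrunken estimate and avoidable Type II error at an elimination step. The stated power for a ratio of .89 is undocumented for this coefficient, but not shown to be wrong.

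**What to change.** Define the Step 1 effect as the framing or mindset contrast over the post-randomisation occasions. One option is the average of post-intervention, 1-month and 3-month (3-month only for the DASS); a single-time contrast would also remove the dilution. Either enter the baseline value as a covariate, or fit a mixed model with a common baseline mean across conditions.

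Restate the power for a ratio of .89 for that contrast, giving the occasion, dispersion, within-person correlation, retention and n per level. Reconcile the weekly base rate with the past-month measure in the same paragraph.

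No new data are needed, since baseline is already collected. The decision rules have been revised once and data collection was due to finish in April 2024, so the change should be dated and recorded as made before any unblinded analysis. Procedures states that investigators and staff do not know individual conditions, which makes this possible. One small cost: the covariate version drops participants with no follow-up, whereas the common-baseline version keeps them.

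### The harm check is missing from the Step 1 fallback and from the Step 2 linear-contrast branch, so an enhancement that helps one co-primary outcome and significantly worsens the other can be selected

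*Combined protocol and SAP*

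**What the plan says.** The Decision Rules define significance as p < .10. A negative coefficient on PTSD or HED is a benefit.

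- **Rule 1, main route:** "We will retain any enhancements for further consideration in Step 2 that have significant negative main effects for both outcomes".
- **Rule 1, fallback:** where no enhancement meets that test, "we will retain enhancements with significant negative main effects on PTSD or HED alone". Nothing is asked of the other co-primary outcome.
- **Rule 2, scope:** interactions of framing, mindset and time are examined for PTSD and HED "among any enhancements with significant negative main effects".
- **Rule 2, contrast branch:** "If there is one or more negative interaction terms, we will examine linear contrasts among the combinations of enhancements that are part of the interaction". The purpose is to see whether adding an enhancement improves matters. Which outcome must improve is not said. The next sentence begins "If this does not yield a clear conclusion in terms of the combination of effects to select" and turns to secondary outcomes and participant satisfaction.
- **Rule 2, other branch:** "If there are no negative interaction terms, we will select any enhancements that had significant main effects and no evidence for negative impacts on outcomes".

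The last sentence holds the only exclusion for harm in rules 1 to 4. Assessing Differences by Condition leaves the coding of time open.

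**The concern.** The rules choose the condition that goes forward to a further randomised trial in people with both PTSD symptoms and heavy drinking. A rule that accepts benefit on one co-primary outcome should look at the other before the choice is final. Here that look depends on which Step 2 branch the data lead to.

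Two wording problems add to the gap. The exclusion has no threshold and does not say which outcomes count. Also, negative means benefit when applied to main effects and harm when applied to impacts, while rule 3 uses positive for the wanted direction. Two analysts could apply the rules to the same data and select different conditions.

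**Working it through.** **The plan's own figure.** The documents give no figure for how often a Step 2 branch is reached. The nearest stated result is in Power: power above .80 for a count ratio of 0.82, with base rate 5.93, n = 75 per condition and alpha .05. With a Poisson Wald test on the log ratio:

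- SE = √[1/(75 × 5.93) + 1/(75 × 5.93 × 0.82)] = 0.0706
- |ln 0.82| / SE = 0.1985 / 0.0706 = 2.81
- Power = Φ(2.81 − 1.96) = 0.80

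The figure reproduces. It neither supports nor weakens this point.

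**Inputs for the branch frequencies.**

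- From the documents: two framing contrasts, one mindset contrast, two outcomes, four assessments, p < .10.
- Number of three-way terms: 2 × 1 × 2 = 4 with linear time, 8 with quadratic time, 12 with categorical time. With one framing: 2, 4 or 6.
- Assumed: two-sided tests (5% in each direction); jointly normal test statistics; correlation 0.5 between framing contrasts, 0.5 between time contrasts, and 0 to 0.5 between outcomes. Branch frequencies come from simulation.

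**Step A. Chance of reaching the branch with the harm check, no true interaction.** For one framing, linear time and uncorrelated outcomes, this can be done by hand: 0.95 × 0.95 = 0.90 if a term must be significant, and 0.5 × 0.5 = 0.25 if any negative sign counts.

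| Terms examined | Significant at p < .10 | Any negative sign |
|---|---|---|
| One framing, linear (2) | 0.90–0.91 | 0.25–0.33 |
| One framing, categorical (6) | 0.78–0.80 | 0.06–0.12 |
| Two framings, linear (4) | 0.83–0.85 | 0.11–0.18 |
| Two framings, quadratic (8) | 0.72–0.75 | 0.03–0.07 |
| Two framings, categorical (12) | 0.64–0.68 | 0.01–0.04 |

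The complements give the bypass rates: 1 − 0.91 to 1 − 0.64, about 9–36%, if significance is required; 1 − 0.33 to 1 − 0.01, about 67–99%, if sign alone counts. With one true synergy as large as a main effect that has 80% power, the significance reading bypasses the check in about 36–41% of trials (linear time) or 61–68% (categorical time).

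**Step B. Chance that an enhancement helping one outcome and harming the other passes Step 1.** With no effects at all and uncorrelated outcomes, one enhancement shows significant benefit on one outcome and significant harm on the other with probability 2 × 0.05 × 0.05 = 0.005. Across three contrasts and outcome correlations of 0 to 0.3, simulation gives 0.003–0.015.

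Now assume a trade-off: one framing truly lowers HED and truly raises PTSD scores, each with 80% power, and there is no true interaction. Then 0.8 × 0.8 = 0.64, and simulation gives 0.61–0.64.

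**Step C. Passing Step 1 and also bypassing the check.** If the terms for both framings are examined whichever enhancements were retained:

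- Significance reading: 0.61 × (1 − 0.84) = 0.10 up to 0.64 × (1 − 0.64) = 0.23
- Sign reading: 0.61 × (1 − 0.15) = 0.52 up to 0.64 × (1 − 0.01) = 0.63

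If only retained pairs are examined, mindset must also pass Step 1. With no true mindset effect and uncorrelated outcomes it does so with probability 1 − 0.95² = 0.0975, so a pair exists with probability about 0.64 × 0.0975 = 0.062. The bypass is then:

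- Significance reading: 0.062 × (1 − 0.90) = 0.006 to 0.062 × (1 − 0.78) = 0.014
- Sign reading: 0.062 × (1 − 0.25) = 0.047 to 0.062 × (1 − 0.06) = 0.058

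**The case against.** The strongest reply is that the plan already contains the safeguard. Rule 1 only retains an enhancement for further consideration, and Step 2 then excludes those with evidence of harm. A reader might infer from the sign-only column that this exclusion is rarely reached. The documents do not support that. The rules set their own criterion of p < .10, and rule 3 speaks of significant interactions. On that reading the branch with the check is the usual one when no interaction exists, at about 64–91%. If interactions are examined only among retained enhancements and no framing-plus-mindset pair survives Step 1, there is no interaction to test and the check always applies. All of this stands.

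It can also be said that the contrasts ask about improvement within a step that covers both PTSD and HED, so opposed effects might count as unclear. But the tie-breaker then looks at secondary outcomes and satisfaction, not at the other co-primary outcome. This is no exclusion for harm.

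Finally, a reader might take the bypass rates as the chance of selecting a harmful enhancement. They are not. That needs a benefit on one outcome together with harm on the other, and nothing in the documents predicts this.

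**Conclusion.** The concern holds as a gap in the rules. Step 1 can carry forward an enhancement that significantly worsens one co-primary outcome, and the contrast branch can then select it, alone or in combination, without any check for harm. The open meaning of the trigger decides whether the check is bypassed in a minority of trials or in most of them when no interaction exists.

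The practical risk is small if there are no real effects, because such an enhancement passes Step 1 in only about 0.3–1.5% of trials. In the assumed trade-off it is material (0.10–0.23 on the significance reading, 0.52–0.63 on the sign reading) if all interaction terms are examined. It falls to about 0.01 and 0.05–0.06 if only retained pairs are examined and mindset has no effect. These sizes rest on the assumed correlations, effect sizes and two-sided tests. The gap itself rests only on the wording of rules 1 and 2.

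**What to change.** 1. Add to rule 1: *An enhancement retained on one co-primary outcome alone is dropped if its effect on the other co-primary outcome is in the worsening direction with p < .10.*
2. Apply the same check to any combination chosen by the Step 2 contrasts, and name the comparator (for example, no framing with simple reminder).
3. State that the Step 2 trigger means an interaction significant at p < .10 in the beneficial direction, and whether terms are examined only among retained enhancements.
4. In the last sentence of rule 2, write *worsening of* in place of *negative impacts on*.

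With item 1, the chance of carrying forward an enhancement with significant benefit on one co-primary outcome and significant harm on the other in the main-effects model becomes zero by construction. Harm too small to reach p < .10 would still pass.

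The cost is a few sentences, using estimates from the models already planned. The downside is about a 5% chance per check (one direction of a two-sided .10 test) of dropping an enhancement that has no true effect on the other outcome. The change should be fixed before outcomes are examined by condition.
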